1.2.2.1.2. Pigs

This study was conducted to evaluate the potential local and systemic toxicity as well as efficacy of the test article, RZL-012 (50 mg/mL), in domestic Yorkshire crossbred swine following subcutaneous injection into the subcutaneous abdominal fat on Day 0. Methods and results from the extended single dose toxicity in pigs study are described in detail in the IB.

Assessment of toxicity was based on mortality, clinical observations, body weight, qualitative food consumption, body temperature, subcutaneous fat temperature, blood pressure, physical and electrocardiographic examinations, and anatomic and clinical pathology. Blood samples were collected and analyzed for porcine stress syndrome testing and toxicokinetic assessment of the test article.

Administration of the test article was not associated with any mortality, clinical observations (with the exception of transient redness and swelling at injection sites), body weight or food consumption changes, effects on electrocardiographic endpoints, or changes in clinical chemistry or coagulation parameters. It should be noted that three animals died during the post anesthesia recovery period. The cause of death was considered to be related to perioperative complications associated with the anesthesia and not related to RZL-012 or saline administration. These three animals were replaced on study. This nonclinical laboratory study was conducted in accordance with the United States Food and Drug Administration (FDA) Good Laboratory Practice (GLP) Regulations, 21 Code of Federal Regulations (CFR) Part 58 and the Organization for Economic Cooperation and Development (OECD) Principles on GLP [as revised in 1997; ENV/MC/CHEM(98)17]. A complete postmortem necropsy was conducted on these dead pigs, and protocol-designated tissues were saved and processed for microscopic evaluation under ambient conditions to Alizée Pathology, Thurmont, Maryland. Two of these animals were controls and one treated. Pigs are very sensitive to anesthesia and these were complications due to it. Attached is the study report - you can find mortality results and discussion on page 26-27.

A slight elevation in body temperatures was noted in males treated with the test article from Days 14-16 until Days 77-79. In addition, several animals were observed with perioperative hyperthermia and/or hypothermia. To determine if the perioperative hyperthermia and/or hypothermia was caused by Porcine Stress Syndrome all remaining animals on study were tested and determined to be normal (negative).

Administration of the test article was associated with changes in subcutaneous fat temperatures, a mild increase in neutrophils, and macroscopic and microscopic observations.

A noticeable difference in subcutaneous fat temperatures was noted between treatment groups. Beginning as early as Day 4-5, an increase in temperature was noted at all test article treated sites

in both males and females. The increase in temperature was noted through Days 58-63. At study termination, subcutaneous fat temperatures at treated sites were comparable to vehicle control.

Subcutaneous administration of RZL-012 (50 mg/mL) to farm pigs resulted in mild increases in neutrophils in both sexes at the 24-hour post-dose collection, which were most typical of an inflammatory response. Increases in neutrophils had resolved by the Day 14 collection.

Analysis of the plasma samples following subcutaneous administration of RZL-012 (Group 4) found that both female and male farm pigs were exposed to RZL-012. Mean systemic exposure (area under the concentration versus time curve between zero and the 24 hour time point [AUC_{0-24hr}]) and maximum observed concentration (C_{max}) values, were 3700 (hr*ng/mL) and 529 (ng/mL), respectively, for males and mean systemic exposure (AUC_{0-24hr}) and C_{max} values, were 2940 (hr*ng/mL) and 528 (ng/mL), respectively, for females.

Upon evaluation of the injection site photographs, no irritation was observed but transient redness was noted. Upon microscopic evaluation at 24 hours and 14 days, test article related findings in the injected subcutaneous tissue was noted. These findings were characterized by necrosis of the subcutaneous fat and muscle accompanied by acute inflammation at 24 hours post-dose. At 14 days, residual necrotic tissue in the injected areas was noted with evidence of on-going healing characterized by chronic inflammation and fibrosis. There was no evidence of systemic toxicity at 24 hours or 14 days

The 14 day interim results of this study demonstrated that administration of 5.68 to 7.14 mg/kg to males and 5.32 to 6.33 mg/kg to females of RZL-012 (test article) over 20 injection sites in the pig was associated with expected changes in subcutaneous fat temperatures, transient changes in neutrophils, and marked localized irritation and tissue necrosis. The increase in subcutaneous fat temperature was considered to be related to the mechanism of action of RZL 012, and an indication of the efficacy of the test article. The microscopic changes noted at 24 hours were beginning to resolve at 14 days. The results of the final time point at 84 days will allow for assessment of the resolution of these findings.

1.2.3. Additional Nonclinical Studies

- Secondary pharmacology (searching for off-target receptors).
- Establishing pharmacokinetic (PK) parameters and investigation of RZL-012 metabolism by liver enzymes and half maximal inhibitory concentration (IC₅₀) in cell-culture.
- Testing RZL-012 mutagenicity, utilizing the Ames test.
- Pyrogenicity in rabbits.
- Assessment of RZL-012 binding to the β 3 receptor in cellular and nuclear receptor functional assays.

- Assessment of RZL-012 uptake by the 5-HT neurotransmitter in the absence and presence of a 5-HT_{2B} agonist.
- Assessment RZL-012 effect on 5-HT neurotransmitter uptake and release in cellular and nuclear receptor functional assays.
- ADME-Toxicology
- Genotoxicity

Methods and results from these safety studies are described in the Investigator's Brochure.

1.2.4. Clinical Studies

Raziel Therapeutics has conducted an Exploratory phase 0, randomized, double-blind, vehicle-controlled study aimed at the evaluation of safety and thermogenesis-induction of three escalating doses of RZL-012 drug product in overweight and obese volunteers. In each cohort, 8 subjects were enrolled, 6 active and 2 control. Study design is presented in the following table:

Table 1: Phase 0 Clinical Trial Design

	Cohort 1	Cohort 2	Cohort 3
Number of Subjects – Active/Placebo	6/2	6/2	6/2
Total Dose RZL-012 (mg)	5	10	20
Dose per NOAEL*	1/50 th	1/25 th	1/12.5 th
Number of Injections	1	2	4

Primary objective: Evaluation of the overall safety of RZL-012 subcutaneous injection and the existence of a thermogenic effect.

Secondary objective: Determination of RZL-012 pharmacodynamics and pharmacokinetics. Evaluation of the extent, duration and tissue associated changes of the thermogenic response to RZL-012, via minimal invasive means including injected-site thermogenesis imaging, MRI, and punch biopsy following injection into the subcutaneous fat.

Primary Endpoints:

Safety - The primary safety endpoint was no more than two subjects experiencing a dose-limiting toxicity (DLT) event.

Efficacy - The primary efficacy endpoint was a significant thermogenesis at the injected site compared with the contra-lateral, non-injected site. This was monitored by sensitive (± 0.1 °C) infra-red thermal camera. A thermogenic effect was defined by an increase of 1 °C in the injected site when compared to the surroundings and/or the contra-lateral (non-injected site), apparent at least 28 days after injection and non-related to inflammatory response as determined

by inflammatory cytokines. The primary efficacy evaluation was supported by results from secondary endpoints, including MRI, biopsy, and biomarkers.

Secondary Efficacy Endpoints:

1. The key secondary efficacy endpoint was the duration of the thermogenic effect in those subjects demonstrating clear thermogenesis by 28 days after injection.
2. Local reduction in fat mass as determined by MRI.
3. Clinical laboratory changes, including improvement in fasting blood glucose and lipid profile.
4. Anthropometric changes, including body weight change.
5. Establishing pharmacokinetic profile for RZL-012
6. Elucidation of the histological changes account for the thermogenic effect by biopsy of the injection site.
7. Exploration of mode of action by evaluation of inflammatory markers and cytokines

Results:

This was a dose escalation exploratory clinical trial of RZL-012, a first-in-class, new chemical entity.

RZL-012 was generally found to be safe in all cohorts. There were no clinically significant changes in vital signs, ECG and almost all blood laboratory tests. Most adverse events (AEs) associated with RZL-012 injection occurred confined to the injection site and were transient. Biopsy from the injected site revealed no damage to the skin 56 days following RZL-012 injection. The only significant local AE was an abscess in one subject in the lower abdomen on the injected side, but at a considerable distance from the site of injection.

In another patient, a severe elevation of alanine aminotransferase (ALT) blood levels and a moderate elevation of AST blood levels were seen 14 days following injection. This elevation was transient (resolved within 14 days). In light of the pre-clinical findings (increased AST blood levels in female rats sacrificed on Day 2 following RZL-012 injection) and in light of the findings in this clinical trial, Raziel therefore plans to monitor closely (on 24hr, Day 3, Day 7, Day 14, Day 21, Day 28 and will follow further if necessary) liver functions in the next clinical trial. There were no other systemic clinically significant AEs.

The exploration of thermogenesis induction by RZL-012 in humans was successful. A raise in temperature at the injection site was mostly evident in cohort 3 (the highest dose) at Day 14 or Day 21 following injection in RZL-012 treated subjects only. This change in temperature was captured and recorded by the infra-red camera.

Although not statistically significant, a drop in the change from baseline in SFM ratio (treated/control) over time by MRI in RZL-012 treated subject of cohort 3 was evident in 5 of 6 treated subjects. The drop in subcutaneous fat associated with a drop in weight (more than 1 kg) and Body Mass Index (BMI) when compared to baseline and is evident in 4 of 6 RZL-012 treated subjects of cohort 3 on Day 28 and/or Day 56, while controls gained weight and increased BMI.

Biopsy did not yield enough tissue (because punch biopsy did not penetrate deep enough to reach the remodeled tissue), and therefore, it was not possible to demonstrate that thermogenesis is due to adipose tissue remodeling.

Although not statistically significant, a decrease in TC and FFA blood levels was evident in subjects of the RZL-012 treated group in cohort 3. This may imply to the mode of action of RZL-012 as stimulation of a thermogenic tissue such as BAT, is known to cause a systemic effect via the mobilization of glucose and FFA from the blood stream to feed the ongoing local thermogenesis. Thus, lipolysis of WAT triacylglycerols (TAG) stores is accelerated and the uptake of FFA derived from blood-borne lipoproteins is increased due to the action of lipoprotein lipase (LPL). Raziel assumes that circulating FFA utilization by the RZL-012-induced thermogenic tissue resulted in lower levels of FFA in the blood, a process that may be beneficial for health. There was no consistent pattern to suggest a connection between inflammation markers and cytokines levels and changes in thermogenic activity reflecting the intended effect of the drug as opposed to local inflammation and distinguish between events related to M1 and M2 macrophages. Though, an increase in Adiponectin blood level was evident at Day 21 and Day 28 in 3 of 6 subjects treated with RZL-012, but not in controls. Adiponectin was found to be an obligatory mediator of cold-induced browning of WAT (9). Adiponectin can be elevated under various conditions, including those that trigger tissue remodeling in favor of thermogenesis such as chronic cold exposure. Although we do not know what triggered elevation of adiponectin in this study, it is known that downstream effects of adiponectin can promote the type of tissue remodeling we are expecting.

Raziel concludes that the potential risk-benefit balance for RZL-012 is favorable, and that it is likely that higher doses of RZL-012 will generate better results. This will be assessed in the next clinical trial.

Methods and results of this exploratory study are described in the IB.

2. PURPOSE AND STUDY OBJECTIVES

2.1. PURPOSE

An open label, phase 2a clinical trial for the evaluation of safety and efficacy of RZL-012 for the treatment of women with lipedema involving substantial fat above the knee or women and men with nodular Dercum's disease.

2.2. STUDY OBJECTIVES

2.2.1. Primary

The primary objective is the evaluation of the overall safety of RZL-012 following injection into the subcutaneous fat in patients with lipedema.

2.2.2. Secondary

The secondary objective is the evaluation of local fat reduction, its extent, duration and tissue associated changes and the extent of pain relief, in response to RZL-012 treatment, utilizing minimal invasive means (ultrasound) following subcutaneous injection of RZL-012 into fatty tissue below the skin.

3. STUDY DESIGN

3.1. DESCRIPTION OF STUDY DESIGN

This is an open label, 2 cohort, clinical trial in women with lipedema with substantial fat above the knee or women and men with nodular Dercum's disease. Each cohort will have 6 subjects who will receive RZL-012.

3.2. DOSE RATIONALE

The initial dose was determined by the NOAEL established by the Good Laboratory Practice (GLP) extended single dose toxicology study and by the previous phase 0 clinical trial in which 20mg RZL-012 was the highest dose achieved. This initial study is an escalating dose study. If no more than 1 subject experiences intolerable side effects within 14 days following the injection of the last dosed group, according to schedule, an additional cohort of volunteers will be administrated the next dose level.

Cohort 1- will be comprised of subjects with Dercum's disease. All subjects will be injected with RZL-012. Dosing will be calculated according to the size of the nodule (diameter) as determined by ultrasound: 5mg/cm² reaching a maximal dose of 40 mg RZL-012 per subject (1/6.25 the NOAEL based on the Human Dose Equivalent [HED] GLP Toxicology studies).

Cohort 2 - will be comprised of subjects with lipedema with substantial fat above the knee and will be conducted in a dose escalation manner.

The first 3 subjects will receive 60mg RZL-012 (1/4.688th the NOAEL based on HED from GLP toxicology study).

The last 3 subjects will receive 80mg RZL-012 (1/3.125th the NOAEL based on HED from GLP toxicology study).

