
Study Drug Dosage and Administration
	
The 1st cohort will be comprised of subjects with Dercum's disease: all subjects will be injected with RZL-012. Dosing will be calculated according to the size of the nodule (diameter) as determined by ultrasound: 5mg/cm² reaching a maximal dose of 40mg per subject (1/6.25 the No observed adverse effect level [NOAEL] based on Human Equivalent Dose [HED] from Good Laboratory Practice [GLP] toxicology study).
 
Nodule of 2-2.9cm diameter, as determined by ultrasound, will be injected 2 injections (0.1 mL each, 1 cm apart); total of 10 mg RZL-012.
 
Nodules of 3-3.9cm diameter, as determined by ultrasound, will be injected 3 injections (0.1 mL each, 1 cm apart); total of 15 mg RZL-012.
 
Nodules of 4-8cm diameter, as determined by ultrasound, will be injected 4 injections (0.1 mL each, 1 cm apart); total of 20 mg RZL-012.
 
  
 Cohort 1	
   
 Number of Subjects – Active	6	
 
 Nodule size – diameter (cm)	2-2.9	3-3.9	4-8	
 
 Total Dose of RZL-012 (mg)	10	15	20	
 
 Dose per NOAEL*	1/25th	1/18.75th	1/12.5th	
 
 Number of Injections	2	3	4	
  
 
Subjects will receive a single treatment in multiple sites (2-8) of injection according to the design in the picture below:
 
 
  
Lipoma size: 2-2.9cm 2 injections of RZL-012
 
 
  
Lipoma size: 3-3.9cm 3 injections of RZL-012
 
 
  
Lipoma size: 4-8cm 4 injections of RZL-012
 
 
	Cohort 1				Number of Subjects – Active	6			Nodule size – diameter (cm)	2-2.9	3-3.9	4-8	Total Dose of RZL-012 (mg)	10	15	20	Dose per NOAEL*	1/25 th	1/18.75 th	1/12.5 th	Number of Injections	2	3	4
Cohort 1																									
Number of Subjects – Active	6																								
Nodule size – diameter (cm)	2-2.9	3-3.9	4-8																						
Total Dose of RZL-012 (mg)	10	15	20																						
Dose per NOAEL*	1/25 th	1/18.75 th	1/12.5 th																						

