Number of Injections	2	3	4																						

Injections will be diagonally (45 °) to the skin surface and towards the center of the nodule and the distance between injections in a nodule will be 1 cm (see picture below).

The 2nd cohort will be comprised of subjects with lipedema with substantial fat above the knee. The first 3 subjects will receive 30 mg RZL-012 in 6 injections (0.1mL each) in one leg followed by 30mg RZL-012 (6 injections, 0.1mL each) in the second leg adding up to 12 injections of 60mg RZL-012 (1/4.688th the NOAEL based on HED from GLP toxicology study). The last 3 subjects will receive 40mg RZL-012 in 8 injections (0.1mL each) in one leg followed by 40mg RZL-012 (8 injections, 0.1mL each) in the second leg adding up to 16 injections of 80mg RZL-012 (1/3.125th the NOAEL based on HED from GLP toxicology study).

Cohort 2		
Number of Subjects – Active	3	3
Total Dose RZL-012 (mg)	60	80
Dose per NOAEL*	1/4.688	1/3.125
Number of Injections	12	16

* based on HED from GLP toxicology study

A grid line will be drawn with a makeup pencil in a horizontal plane (Figure 2) 4-6 cm from the suprapatellar fat and its distance from the floor recorded. An attempt should be made to find palpable nodules along the grid line. The injection sites will be marked in circles with a non-erasable pen. This mark should be intensified upon following visits. Injections will be given in multiple sites (4-8 in each leg), diagonally (45 °) to palpable nodules, in the fat above the knee. An attempt should be made to lift the nodule and inject into the middle of the fat-mass. If no nodules are noted in the horizontal plane, drug will be injected in to the fatty tissue (in this case small nodules seen in ultrasound will be followed for changes). Injections will be on the same horizontal plane.

	
Injections will be spread as much as possible and the distance between injected sites will be at least 2-3 cm, according to the number of injections (see picture below).
  
12 injections of RZL-012 16 injections of RZL-012

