1.2.2.1. Extended Single Dose Toxicity Studies

1.2.2.1.1. Rats

Single subcutaneous administration of test item RZL-012 at the doses of 5, 10, and 20 mg/kg in Sprague-Dawley rats resulted in non-systemic effects and or local effects at the treated skin area. Few changes observed in haematological parameters (white blood cells [WBC] count, neutrophils, monocytes and eosinophils) were considered secondary effects due to inflammatory response (local skin reactions). The changes observed in clinical chemistry parameters (increased blood urea nitrogen [BUN] in males and females and increased creatinine and aspartate aminotransferase [AST] levels in females) at all the doses tested and histopathological changes in kidneys (necrosis in tubular epithelium) at 20 mg/kg were considered systemic effects. Methods and results from the extended single dose toxicity study are described in the Investigator's Brochure (IB).

Considering skin changes as non-systemic effects and or local effects, the NOAEL was determined at 5 mg/rat with an average body weight of 258.9 g, under the test conditions and doses employed.

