Injections will be spread as much as possible along the grid line and the distance between injected sites (Figure 4) will be:

- At least 3 cm - For subjects receiving 8 and 12 injections.
- At least 2cm - For subjects receiving 16 injections.

Figure 4: RZL-012 Injection Sites in Lipedema Subjects

In lipedema subjects study will be performed in a dose escalation manner:

The first 2 subjects will receive 20mg RZL-012 in 4 injections (0.1mL each) in one leg followed by 20mg RZL-012 (4 injections, 0.1mL each) in the second leg adding up to 8 injections of 40mg RZL-012 ($1/6.25^{\text{th}}$ the NOAEL based on HED from GLP toxicology study).

The next 2 subjects will receive 30mg RZL-012 in 6 injections (0.1mL each) in one leg followed by 30mg RZL-012 (6 injections, 0.1mL each) in the second leg adding up to 12 injections of 60mg RZL-012 ($1/4.688^{\text{th}}$ the NOAEL based on HED from GLP toxicology study).

The last 2 subjects will receive 40mg RZL-012 in 8 injections (0.1mL each) in one leg followed by 40mg RZL-012 (8 injections, 0.1mL each) in the second leg adding up to 16 injections of 80mg RZL-012 ($1/3.125^{\text{th}}$ the NOAEL based on HED from GLP toxicology study).

Within each cohort, dosing of the subjects will progress consecutively from one individual to the other with a minimum of 7-days between subjects to assess safety. This study design will allow the physicians to monitor safety for at least 7 days prior to dosing the next subject. For cohort 2 the decision to proceed to the next dose level will be made after reviewing all safety data collected by Day 14 within 2 ± 1 d of the last dosed subject. The trial will proceed within a cohort provided that no more than one subject experiences intolerable side effects in a cohort, and based on the decision made by the PI and the Medical Monitor.

Each RZL-012 kit contains 1 vial (250 mg/5 mL) corresponding to the number of subjects receiving treatment in each cohort.

RZL-012 will be injected on baseline study visit.

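### The NOAEL margins printed for 60 mg and for the 15 mg nodule dose are miscalculated and overstated by 12.5%; the rat dose units also need checking

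*Protocol*

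**What the plan says.** The plan expresses each dose as a fraction of the human equivalent of the NOAEL. It never prints that human dose in milligrams.

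- **60 mg (lipedema):** protocol 3.2 has "The first 3 subjects will receive 60mg RZL-012 (1/4.688th the NOAEL based on HED from GLP toxicology study", and the protocol synopsis has "12 injections of 60mg RZL-012 (1/4.688th the NOAEL based on HED from GLP toxicology study". The same 1/4.688 appears in protocol 3.3.1 and 6.2.3.1 and in SAP 5.2.4 and 5.4.1.3.
- **80 mg (lipedema):** protocol 3.2 has "The last 3 subjects will receive 80mg RZL-012 (1/3.125th the NOAEL based on HED from GLP toxicology study".
- **40 mg (Cohort 1 subject maximum):** the synopsis describes dosing "reaching a maximal dose of 40mg per subject (1/6.25 the No observed adverse effect level". Section 6.2.3.1 gives the same fraction for a lipedema level "adding up to 8 injections of 40mg RZL-012".
- **10, 15 and 20 mg (per nodule, Cohort 1):** the tables in the synopsis and 3.3.1 give 1/25, 1/18.75 and 1/12.5.
- **5, 10 and 20 mg (phase 0):** Table 1 in 1.2.4 gives 1/50, 1/25 and 1/12.5.

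On the animal data, section 1.2.2.1.1 describes administration "at the doses of 5, 10, and 20 mg/kg in Sprague-Dawley rats", then states the NOAEL as 5 mg/rat at a mean weight of 258.9 g. Section 7.2 relates the rat kidney findings to a dose 25 times this study's highest, without saying on what basis the doses were compared.

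**The concern.** All the fractions are presented as shares of the same NOAEL-based dose, so dose times denominator should be constant. For two levels it is not, and both err in the favourable direction. The 60 mg level matters more. It is the first lipedema dose in section 3.2, where the previous human experience is summarised as "20mg RZL-012 was the highest dose achieved", so it is a threefold step (60/20 = 3), and the printed margin is part of the stated rationale for it.

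The rat data raise a separate question. A NOAEL in mg/rat cannot be set against doses in mg/kg without conversion, and the conversion places it almost at the dose that caused kidney necrosis. A reader who wants to trace the safety argument back to the toxicology cannot do so from this text.

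**Working it through.** **Margins.** Implied base = dose × printed denominator; denominator on the common base = 250 / dose.

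| Dose (mg) | Printed denominator | Implied base (mg) | 250 / dose | Printed ÷ 250-based |
|---|---|---|---|---|
| 5 | 50 | 250 | 50 | 1.000 |
| 10 | 25 | 250 | 25 | 1.000 |
| 15 | 18.75 | 281.25 | 16.67 | 1.125 |
| 20 | 12.5 | 250 | 12.5 | 1.000 |
| 40 | 6.25 | 250 | 6.25 | 1.000 |
| 60 | 4.688 | 281.3 | 4.167 | 1.125 |
| 80 | 3.125 | 250 | 3.125 | 1.000 |

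The two odd values are reproduced exactly by averaging the neighbouring denominators:

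- between 40 and 80 mg: (6.25 + 3.125)/2 = 4.6875, printed as 4.688;
- between 10 and 20 mg: (25 + 12.5)/2 = 18.75.

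A denominator is base/dose, so it is not linear in dose. With neighbours d and 2d and a middle dose of 1.5d, averaging gives 0.75 × base/d, while the correct value is base/(1.5d). The ratio is 0.75 × 1.5 = 1.125, which explains why both margins are out by the same 12.5%.

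**Rat units (1.2.2.1.1).**

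- NOAEL: 5 mg / 0.2589 kg = 19.3 mg/kg.
- Top dose as printed: 20 mg/kg × 0.2589 kg = 5.18 mg/rat.
- Gap: (20 − 19.31)/20 = 3.4%.

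Read literally, the NOAEL lies 3.4% below the dose with tubular necrosis and is not one of the doses tested. If the doses were really 5, 10 and 20 mg/rat, the NOAEL would be the lowest dose. The 10 mg/rat dose in 1.2.1.2 points that way but does not prove it.

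**The multiple of 25 (7.2).** The answer depends on assumptions that the documents do not settle.

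- *If the rat NOAEL underlies 250 mg and the rat doses are in mg/rat:* necrosis dose = 250 × 20/5 = 1000 mg. That is 1000/40 = 25 times 40 mg and 1000/80 = 12.5 times 80 mg.
- *If the rat NOAEL underlies 250 mg and the units are as printed:* 250 × 20/19.31 = 258.9 mg, or 258.9/80 = 3.2 times 80 mg.
- *If mg/kg is compared directly, without species scaling, at an assumed weight of W kg:* 20/(80/W) = W/4, which gives 15 at 60 kg, 20 at 80 kg, 25 at 100 kg and 30 at 120 kg.

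Separately, 1.2.2.1.1 reports the BUN and creatinine rises at every dose tested, and the lowest is 5/20 = a quarter of the highest. This holds on any basis.

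**The case against.** The strongest reply is that little depends on these figures. The smallest margin, at 80 mg, is consistent with the common base. The corrected 60 mg margin (1/4.17) is still wider than 1/3.125. Escalation rests on Day 14 safety review, section 3.2 also relies on the phase 0 experience, and no analysis uses the fractions. All of that stands, and it is why the point is minor.

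The 15 mg figure carries even less weight. It is a dose per nodule, and eligibility requires at least two nodules of at least 2 cm, so the lowest planned subject total is 2 × 10 = 20 mg. The 15 mg margin therefore describes no subject's exposure, and the Cohort 1 subject maximum (40 mg, 1/6.25) is consistent.

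The 250 mg base is inferred, not stated. Taking 281.25 mg instead would make five dose levels wrong rather than two (80 mg would become 281.25/80 = 3.52), and the midpoint pattern would be left as a coincidence. The inference is strong but should be confirmed.

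A reader might also infer that the multiple of 25 in 7.2 is wrong and should be 12.5. The documents do not support this. They describe toxicology in two species, the pig study is the one expressly said to follow GLP, and nothing says which species gave the 250 mg. An unscaled mg/kg comparison gives exactly 25 for 80 mg at an assumed 100 kg. For the same reason, it goes too far to say that the unit conflict undermines every fraction. Finally, the sentence in 7.2 can be read as attaching the multiple to the necrosis alone. That leaves a request for clearer wording about BUN and creatinine, not a demonstrated error.

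**Conclusion.** Minor, but wrong as written. The margins for 60 mg and for the 15 mg nodule dose are each overstated by 12.5%: on a 250 mg base they should be 1/4.17 and 1/16.7. This rests on one assumption, that the five mutually consistent dose levels show the intended base. The pattern indicates a calculation error carried through both documents, not a misprint.

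The mix of mg/kg and mg/rat in 1.2.2.1.1 is a real conflict that only the toxicology report can settle. The multiple in 7.2 lacks a stated basis; whether it is right for 80 mg remains open. None of this shows that a dose is unsafe or that the escalation is unsound.

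**What to change.** 1. Confirm the 250 mg base, then print 60 mg as 1/4.17 in the synopsis, protocol 3.2, 3.3.1 and 6.2.3.1, and SAP 5.2.4 and 5.4.1.3. Print 15 mg as 1/16.7 in the synopsis and 3.3.1, labelled as a per-nodule dose.
2. Check 1.2.2.1.1 against the toxicology report and give the rat doses and NOAEL in one unit.
3. In the same check, verify the multiple in 7.2 against 80 mg and state its basis (species and scaling). Word the sentence so that it does not suggest that the BUN and creatinine rises occurred only at that multiple.

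The cost is a look-up in an existing report and an amendment of printed figures. The stated margins become slightly less favourable.
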